Our team is proposing a 2x2 factorial design randomized controlled trial (RCT) called "Decreasing Alzheimer's Disease and Related Dementias after Delirium-Exercise and Cognitive Training (DDD-ECT)" to evaluate the efficacy of 12 weeks of combined physical exercise and cognitive training on the primary outcome of cognitive function among older ICU survivors who experienced delirium or subsyndromal delirium during their ICU stay. We propose to deliver these interventions via a facilitator-led, small group format using internet-enabled, multiparty-videoconference delivered directly into the participants' homes to achieve the following aims:

**Primary Specific Aim: Determine the effect of the combined physical exercise and cognitive training on the cognitive function of ICU survivors aged 50 and older.** Hypothesis: In comparison to older ICU survivors randomized to attention control or either intervention alone, those randomized to 12 weeks of combined physical exercise and cognitive training will have higher total index cognitive scores as assessed by the Repeatable Battery for the Assessment of Neuropsychological Status (RBANS) at 3 and 6 months post randomization.

**Secondary Specific Aim 1: Determine the effect of the combined physical exercise and cognitive training on physical performance, anxiety and depressive symptoms, and quality of life of ICU survivors aged 65 and older.** Hypotheses: In comparison to older ICU survivors randomized to attention control or either intervention alone, those randomized to 12 weeks of combined physical exercise and cognitive training will have higher physical performance as measured by short physical performance battery (SPPB) and two-minute step test, lower mood and anxiety symptoms as measured by Patient Health Questionnaire (PHQ-9) and Generalized Anxiety Disorder (GAD-7) scale, and higher quality of life as measured by the Medical Outcomes Study 36-item short form (SF-36) at 3 and 6-months post randomization.

**Exploratory Aim 1: To examine the mechanisms of action of combined training.** Hypothesis: At the completion of treatment, the combined intervention group will show reduced serum levels of CRP, IL-1, IL-6, IL-8, TNF- $\alpha$ , S-100 $\beta$ , and GFAP and increased levels of BDNF, VEGF, and IGF-1 compared to the attention control, or either intervention alone groups.

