**Secondary Specific Aim 1:** Separate mixed effects models will be used with repeated measures (SPPB, 2-minutes step, PHQ-9, GAD-7, SF-36 PCS and MCS) as the outcome variables, group, time and interactions between group and time as independent variables while adjusting for stratification variables and other baseline covariates that may be different among the four groups. Significant interactions between group and time in these models would indicate differences in changes of functional outcomes, depressive symptoms, and anxiety levels or quality of life over time among the four groups. Post-hoc analyses will also be conducted following significant interactions in the mixed effects models to compare the combined training group to the other three groups and to determine how early a group difference can be detected and whether the effect extends beyond the training period.

**Exploratory Aim 1:** Changes in the serum levels of CRP, IL-1, IL-6, IL-8, TNF-  $\alpha$ , S-100 $\beta$ , GFAP, BDNF, VEGF, and IGF-1 will be calculated and used as the dependent variables in ANCOVA models with group as the independent variable and adjusting for stratification variables and baseline covariates that are

found to be different among the groups in univariate comparisons. Post-hoc comparisons will be used following a significant group effect to compare biomarker levels in the combined training group to the other three groups.

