Sample Size and Power: Cognitive training had been found to have a moderate effect size of approximately 0.5 SD and the combined training was found to have a larger effect size of 0.9 SD when comparing to the control group in healthy elderly subjects. Assuming effect sizes of 0.4 SD in the cognitive training only group and the exercise only groups at 3 and 6 month post baseline compared to the attention control group and effect size of 0.8 SD in the combined training group at 3 and 6 month post baseline compared to the attention group, a sample size of 60 patients in each group will yield 83% power at detecting a significant group by time interaction in a mixed effect model adjusting for correlations of 0.2 for outcomes measured 3 month apart and correlations of 0.1 for outcomes measured 6 month apart at  $\alpha=0.05$ . The power estimation was conducted using the GLMPower procedure in SAS. To further assume that 30% patients may miss some post-baseline assessments, we will need to enroll a total of 344 patients into the study (86 patients per group). Outcomes in Secondary Aim 1 will also have 83% power to detect effect sizes similar to those described for the Primary Aim. For Secondary Aim 2, we will have 81.7% power to detect an overall treatment effect in changes in biomarkers with effect sizes of 0.31 SD in the cognitive training only and the exercise only groups and 0.62 SD in the combined training groups at  $\alpha=0.05$  using one-way ANOVA and the Power procedure in SAS.

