**Biomarkers:** The conceptual model holds that the cognitive benefit of combined physical exercise and cognitive training is achieved through modulation of physiologic process (Secondary specific aim 2). As a result, we will measure circulating levels of the pro-inflammatory cytokines (IL-1, 6, 8, TNF- $\alpha$ ); the acute-phase reactant (CRP); neurotrophic factors (IGF-1, VEGF, BDNF); and markers of glial dysfunction and astrocyte activation (S-100 $\beta$ , GFAP). Serum marker quantifications will be performed in duplicates using pre-validated commercially available assay kits. Each kit employs 1-2 positive control(s) of known concentration and a negative control in every run. We will follow manufacturer provided established protocols for these assays.

**APOE Collection and Assay:** Genomic DNA will be extracted from blood samples using the DNeasy Blood & Tissue Kit (Qiagen, Inc., Valencia, CA) according to the manufacturer's protocol. Approximately 50ng of genomic DNA will be used for amplification. APOE genotypes will be determined by restriction enzyme digestion of amplified DNA.

**Plasma amyloid-β Aβ42/Aβ40:** As number of recent studies have reported that a low ratio of plasma amyloid-β Aβ42 over Aβ40 is associated with increased Alzheimer's disease risk and greater cognitive decline, we will explore the effect of a low ratio on our intervention. Samples will be analyzed using standard analysis techniques.

**Acute Health Care Utilization:** In addition to patient reported emergency department and hospital admission data, we will use the local data-warehouse to capture all of the data needed to determine utilization. Furthermore, we will also use the data from the Indiana Network for Patient Care (INPC) to complement any data use outside of our health system. INPC is the primary health information exchange in the state of Indiana and it provides data for acute care services from all of the health care systems within the state of Indiana. We will determine the number of emergency department visits and the number of re-hospitalizations during follow-up as well as the diagnoses associated with each utilization episode.

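### The biomarker analysis has no method for results below an assay limit and does not routinely adjust for the marker's own baseline; its 81.7% power assumes every change can be measured

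*Combined protocol and SAP*

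**What the plan says.** Section 2 (Exploratory Aim 1) states the direction expected: "At the completion of treatment, the combined intervention group will show reduced serum levels of CRP, IL-1, IL-6, IL-8", followed by TNF-alpha, S-100beta and GFAP. That makes seven markers expected to fall and three (BDNF, VEGF, IGF-1) expected to rise.

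Section 8 (Exploratory Aim 1) calculates changes in serum level and analyses them by group: "GFAP, BDNF, VEGF, and IGF-1 will be calculated and used as the dependent variables in ANCOVA models with group as the independent variable". The other terms are the stratification variables and any baseline covariates that differ between groups in univariate comparisons. A marker's own baseline level therefore enters only if it happens to differ.

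Section 9 (Biomarkers) describes commercial kits run in duplicate with positive and negative controls, and adds: "We will follow manufacturer provided established protocols for these assays". It gives no detection or quantification limit and no rule for a result below one.

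Section 8 (Sample Size and Power), where this aim is called Secondary Aim 2, says "we will have 81.7% power to detect an overall treatment effect in changes in biomarkers". Relative to control, it assumes 0.31 SD for each single-intervention arm and 0.62 SD for the combined arm. The test is the overall F test of a one-way ANOVA at the 0.05 level.

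**The concern.** A result reported only as below the limit has no number to subtract, so that patient's change depends on a choice the plan does not make. The patient attended and gave blood, so the case is neither death nor withdrawal, the two kinds of missing data that Section 8 anticipates. It also depends on the level itself. For the seven markers expected to fall, a true effect would push more of the combined arm below any fixed limit than of the control arm.

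The ways of handling such values give different answers, and nothing stops the choice being made after the arms are known. A null result for such a marker could then reflect the handling rather than the biology.

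**Working it through.** **1. Reproduce the stated power.** Effects 0, 0.31, 0.31 and 0.62 SD of change come from Section 8. The biomarker sentence gives no group size; the primary aim uses 60 evaluable per arm ("a sample size of 60 patients in each group will yield 83% power").

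- Mean effect = (0 + 0.31 + 0.31 + 0.62)/4 = 0.31.
- Sum of squared deviations = 0.31² + 0 + 0 + 0.31² = 0.1922.
- Noncentrality at 60 per arm = 60 × 0.1922 = 11.532, with 3 and 236 df. Power = 0.8170, an exact match.
- At 86 per arm: 86 × 0.1922 = 16.529, with 3 and 340 df. Power = 0.939, no match.

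So the figure rests on 60 numeric changes per arm. The step from 60 to 86 (60/0.70 = 85.7) allows for missed assessments.

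**2. Simulate below-limit values.** The documents give no below-limit share, correlation or scale. These are assumptions: normal log levels, SD of change 1 natural-log unit, a marker expected to fall, 60 per arm, the plan's effects before censoring, and a limit set so that a chosen share of control values lies below it. The table gives power at baseline-to-3-month correlation r = 0.5, with the same control distribution at both visits.

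| Control share below limit | Pairs dropped | Set to limit | Set to half the limit |
|---|---|---|---|
| 5% | 67% | 78% | 80-81% |
| 10% | 56% | 74% | 77% |
| 20% | 39% | 67-68% | 71-74% |
| 30% | 29% | 59-61% | 66-67% |
| 50% | 15% | 41% | 54% |

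- Dropping, over r = 0.2 to 0.8: power is 68-78% at a 2% share, 45-69% at 10% and 18-44% at 30%.
- Unequal loss: at 10%, with baseline 1 SD above the 3-month level and r = 0.2 to 0.5, about 25-31% of the combined arm is lost against about 11% of control.
- Combined-minus-control difference (true 0.62) when pairs are dropped at 10%: about 0.42-0.51.
- The same difference under substitution: half-limit gives about 0.61-0.66 at 10% or less and about 0.52-0.53 at 30% (r = 0.5). The limit itself gives about 0.51 at 10% and 0.36 at 30%. Limit/√2 gives about 0.30-0.31 at 50%.

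**3. Check the raw scale.** Section 8 names no log. With lognormal levels, a 20% share and full-data power of about 66%, dropping pairs raised the mean difference from 1.05 to 1.46 while power fell to about 46%. Half-limit substitution left power at about 65%.

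**4. Check the alternative.** A left-censored regression of the 3-month log level with baseline as covariate recovers a difference of 0.60-0.64. Its power at shares of 10% to 50% is 97-90% at r = 0.2 and 90-79% at r = 0.5.

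The gain over 82% comes from the covariate. With the SD of change fixed at 1, the level variance is 1/(2(1 − r)), and the residual variance after baseline is (1 − r²)/(2(1 − r)) = (1 + r)/2.

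- r = 0.2: 11.532/0.60 = 19.22. Power with no censoring is about 97%.
- r = 0.5: 11.532/0.75 = 15.38. Power with no censoring is about 92%.

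Censoring then lowers these figures; it does not raise them.

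**The case against.** The strongest reply is that nothing in the documents shows a problem of any size. They predict lower levels, not undetectable ones, and give no kit limit or expected share, so every magnitude above rests on an assumption. That stands. A reader might infer that training is meant to drive markers below detection, or that 81.7% is wrong; the text supports neither.

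A reader might also infer that the plan drops undetectable samples. It does not say so. Section 8 applies intention to treat throughout, lets non-normal variables be transformed or analysed by rank methods, and promises sensitivity analyses by imputation or likelihood. This too stands, but none of it is tied to assay limits, and a log transform does not supply a missing number.

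Nor is shrinkage of the effect general. Half-limit substitution at 10% or less leaves the difference almost unchanged, and dropping pairs on the raw scale can enlarge the mean difference, although power still fell in those runs.

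Finally, one might think a censored model must avoid the change score. Once baseline is a term, censored models of the change and of the 3-month level give the same arm estimate. Overestimation (about 0.63-0.93 against 0.62 in the runs) appeared only when baseline was left out.

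**Conclusion.** The concern holds in a limited form. The plan leaves open how a below-limit marker result becomes an analysis value, and it does not routinely adjust for the marker's baseline level. The 81.7% is right on its own inputs but is conditional on a measurable change for every evaluable patient.

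The consequence depends on the share and on the method. With 10% of control values below the limit, on the log scale, power is about 45-69% if pairs are dropped and about 77-83% with half-limit substitution. At 30-50%, substitution also attenuates the 0.62 SD difference, to about 0.3-0.54 for half-limit or limit/√2. If few samples are undetectable and they are kept, little changes. For the three markers expected to rise, the argument that loss is heavier in the combined arm does not apply.

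The aim is exploratory and the primary and secondary outcomes are untouched, so the priority is low.

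**What to change.** In Section 8 (Exploratory Aim 1):

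- Model the 3-month log level with arm, discharge location and the patient's baseline log level, plus an indicator for an undetectable baseline.
- Record each kit's lower limit. For markers whose below-limit share, pooled over arms and seen blind to arm, exceeds a figure fixed in advance, fit the same model as a left-censored (Tobit-type) regression at that limit.
- Below that figure, keep the samples and use one substitution constant named in advance; half the limit performed best of the constants tried at low shares.
- Where most pooled samples are undetectable, compare arms on detectable yes/no.
- Do not drop below-limit samples.

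In Section 8 (Sample Size and Power), state that 81.7% assumes measurable values at both visits. Credit any gain over 82% to the baseline covariate, not to the censored method.

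The cost is a few sentences before unblinding and a little more analysis work, with no extra samples or visits. The downside is a log-normal assumption for the censored part.

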### **Potential Risks:**

(1) *Fatigue, anxiety, stress, or embarrassment from the training or testing sessions.* Emotional distress may result from answering health and behavior questions. Testing may also create anxiety, stress, or embarrassment at perceived performance. Participants may also become fatigued during the testing and/or training sessions.

(2) *Falls and/or muscle stiffness and soreness from exercise.* The exercise intervention components proposed in this study are consistent with standard recommendations for exercise among older adults. Based on piloting and published studies, the most common risk associated with increased exercise is mild muscle stiffness and soreness. Moderate-intensity physical activities are associated with a very low

risk of musculoskeletal complications. There is a low risk of fall given all exercises in the physical intervention are seated.

(3) *Cardiovascular complications from exercise.* The risks of cardiovascular complications do increase transiently during periods of strenuous physical activity.

(4) *Exposure of confidential information.* There is the potential for loss of privacy or confidentiality due to the data collection efforts of this study.

(5) *Discomfort with biological samples collection.* Two blood samples will be collected from each participant, one during their hospital stay and the other at 3-months follow-up. Drawing blood could be associated with pain, bruising, and anxiety.

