## 8. Statistical Considerations

To verify the comparability of the randomized groups, patients' baseline characteristics among the four groups will be compared using analysis of covariance (ANCOVA) for continuous variables and the Cochran-Mantel-Hansel statistic for categorical variables while adjusting for age group. We will examine the distributions of continuous variables and use alternative approaches such as transformation or nonparametric methods in cases of violation to the normal distribution assumption. We will also examine the frequency distribution of all categorical variables and adopt exact inference procedures in cases of zero or small cell size. All analyses will be conducted using the SAS 9.4 (SAS Institute, Carey, North Carolina).

**Primary Specific Aim:** Mixed effects models will be used with repeated RBANS scores collected at baseline, 3 months and 6 months as the outcome measures, group, time and a group by time interaction as independent variables while adjusting for stratification variables and other potential baseline covariates found to be significantly different in univariate comparisons. A significant interaction between group and time would indicate differences in changes of cognitive functions over time among the four groups. Post-hoc comparisons will be conducted following a significant interaction between group and time to compare the effect of the combined training group to the other three groups (attention control, cognitive training only, and exercise only groups) at 3 month for immediate training effect and at 6 month for sustained training effect. Separate mixed effect models will also be used for repeated, Trail Making A&B, and Stroop Color and Word Test scores.

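### Exploratory biomarker analysis: change in serum level with no log scale and no prespecified adjustment for the marker's own baseline, which is likely to cost much power

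*Combined protocol and SAP*

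**What the plan says.** - **Outcome.** Section 8, Exploratory Aim 1: changes in CRP, IL-1, IL-6, IL-8, TNF-α, S-100β, GFAP, BDNF, VEGF and IGF-1 "will be calculated and used as the dependent variables in ANCOVA models with group as the independent variable". Neither a raw nor a log scale is named.
- **Covariates.** The same paragraph has the models "adjusting for stratification variables and baseline covariates that are" found to differ among the groups in univariate comparisons. The marker's own baseline level is not named.
- **Non-normality.** The opening paragraph of Section 8 has each continuous variable checked for its distribution, with a plan to "use alternative approaches such as transformation or nonparametric methods in cases of violation to the normal distribution assumption".
- **Timing.** Section 6, Potential Risks, item 5, describes two samples, "one during their hospital stay and the other at 3-months follow-up". Section 4, Randomization, ties the first sample to the baseline assessment, which may take place at home after discharge if it cannot be completed in hospital.
- **Power.** Section 8, Sample Size and Power (where the aim is called Secondary Aim 2), claims "81.7% power to detect an overall treatment effect in changes in biomarkers" for "effect sizes of 0.31 SD in the cognitive training only and the exercise only groups" and "0.62 SD in the combined training groups", from a one-way ANOVA at α = 0.05. It gives no marker SD and no correlation between visits.

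**The concern.** Section 1 describes delirium as an inflammatory syndrome with raised cytokines, S-100β and GFAP. A sample taken during the admission would catch those markers high, and to a different degree in each patient. Three months later much of that elevation may have resolved. The arithmetic change would then mostly reflect how high each patient was in hospital, and a training effect on the 3-month level would be small beside that spread.

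The fallback for non-normality does not clearly help. The variable defined for analysis is the change, a negative change has no logarithm, and the plan does not say that levels are logged before differencing.

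At stake is the trial's mechanism aim: a real effect on the markers could be reported as null.

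**Working it through.** **1. The plan's figure.** Inputs from Section 8: means 0, 0.31, 0.31 and 0.62 SD; four groups; α = 0.05. The n of 60 per group is stated for the primary aim and is assumed to apply here.

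λ = n Σ(μᵢ − μ̄)² / SD² = 60 × (0.31² + 0 + 0 + 0.31²) = 60 × 0.1922 = 11.53. The noncentral F with 3 and 236 df gives power 0.8170, which reproduces the 81.7%. (With n = 86 it would be 0.939.)

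**2. What a variable baseline does, without assuming skewness.** Suppose the effects are 0.31 and 0.62 SD of the *3-month level*. Let r = baseline SD / 3-month SD, and ρ = the correlation between visits. In units of the 3-month SD:

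- SD of unadjusted change = √(r² + 1 − 2ρr)
- residual SD with baseline as covariate = √(1 − ρ²), whatever r is

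| r | ρ | SD of change | Power, unadjusted change | Power, baseline as covariate |
|---|---|---|---|---|
| 1 | 0.5 | 1.00 | 81.7% | 91.9% |
| 1 | 0.2 | 1.26 | 59.6% | 83.4% |
| 2 | 0.2 | 2.05 | 25.0% | 83.4% |
| 3 | 0.2 | 2.97 | 13.7% | 83.4% |

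For r = 2 and ρ = 0.2, for example: √(4 + 1 − 0.8) = 2.05, and √(1 − 0.04) = 0.98.

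**3. Skewed markers with a proportional effect.** The documents give no marker data, so these inputs are all assumptions:

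- lognormal levels, log SD 0.6 to 1.0 at both visits, ρ 0.2 to 0.5
- training lowers the 3-month level by 0.31, 0.31 and 0.62 SD of the log change
- baseline at 1, 3 or 10 times the 3-month level
- 60 per arm and 1,500 simulated trials per scenario (simulation standard error at most √(0.25/1500) = 1.3 points)

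The SD of the log change is log SD × √(2 − 2ρ). The combined-arm effect is therefore a ratio between exp(−0.62 × 0.6 × √1.0) = 0.69 and exp(−0.62 × 1.0 × √1.6) = 0.46.

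| Analysis | Baseline 1× | Baseline 3× | Baseline 10× |
|---|---|---|---|
| Raw change, unadjusted | about 38-59% | about 8-13% | about 3-6% |
| Kruskal-Wallis on raw change | about 57-67% | about 15-19% | about 6% |

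The other analyses hardly depend on the elevation: raw change with raw baseline as covariate 63-93%, log ratio 79-85%, log 3-month level with log baseline as covariate 90-97%.

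At a 3-fold baseline, 87-98% of raw changes are negative and so cannot be logged. Ranking them is valid but recovers little. Adding the raw baseline recovers much of the loss, and the log scale recovers the rest.

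**4. Type I error.** With no arm effect, in a lognormal scenario with a strongly raised baseline, every analysis rejected in about 4-6% of trials.

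**The case against.** **The 81.7% is right on its own terms.** The plan defines the effects as SDs of the change. With lognormal data and effects set at 0.31 and 0.62 SD of the *raw change*, simulated power stays at 81-83% for baselines of 1, 3 and 10 times the 3-month level, even with up to 99.9% of changes negative. Skewness alone therefore costs nothing at this sample size. This stands, and a reader who infers that the power figure is miscalculated would be wrong. What remains is that 0.62 SD of a change inflated by hospital variation is a far larger biological effect, and the plan does not justify it.

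**The fallback does not bar a log.** A reader might infer that transformation is impossible here. The documents do not support that: levels are continuous variables, and logging them before differencing fits both paragraphs. The gap is that the order is not stated.

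**Not every baseline is an in-hospital value, and not every marker falls.** Section 4 allows a draw at home. Section 1 describes lower IGF-1 and BDNF in delirium, and Section 2 hypothesises rises in BDNF, VEGF and IGF-1 with training. Mostly negative changes can be expected at most for the inflammatory and glial markers. Both limits stand.

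**Recovery cancels.** Mean recovery common to all arms drops out under randomisation. Variation between patients in recovery does not, and that is what costs power.

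**Conclusion.** The point holds as a gap in prespecification with a likely loss of power. As written, the marker analysis permits an unadjusted raw change from a sample usually taken in hospital.

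For the inflammatory and glial markers, if levels are right-skewed and training acts proportionally, power is about 38-59% with equal baseline and about 8-13% with a 3-fold higher baseline, against 90-97% for a baseline-adjusted log analysis. These figures rest on assumed distributions and elevations. The direction is more secure, because section 2 of the working shows the same pattern without skewness when the hospital value is more variable than the 3-month value.

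The documents do not show bias, an inflated type I error or an arithmetic error in the 81.7%. The aim is exploratory and no primary or secondary conclusion depends on it, so the severity is modest. The change is still worth making because it is nearly free.

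**What to change.** **Section 8, Exploratory Aim 1.** Replace the definition of the dependent variable with: *Each marker is log-transformed at each visit. The dependent variable is the log 3-month level in an ANCOVA with arm, log baseline level and the stratification variable. Arm effects are reported as ratios of geometric means.*

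Log baseline must be in the model. Without it, the log 3-month level and the log ratio to baseline are different analyses with different power. With it, they give the same arm effects.

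**Section 8, Sample Size and Power.** State that the 0.31 and 0.62 SD are on the log scale, and give the SD and correlation behind them.

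**Sections 4 and 6.** Reconcile the two statements on where the baseline sample is drawn.

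**Cost.** Wording only, using data already planned. Effects are read as percentage differences rather than concentration differences.

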Missing Data: Two types of missing data are anticipated in this trial. The first is due to death during follow-up. Our previous studies on ICU survivors have shown that most post-ICU deaths happen within the first 30 days of discharge. We do not expect rates of death to differ among the four randomized groups. The second type of missing data comes from participant withdrawal during follow-up. There may be a potential for higher rate of withdrawal in those enrolled in the intervention groups than in the control group. The mixed effects model approach we propose to use is robust under the missing at random assumption, i.e. the probability of missing is unrelated to the missing observations. We will compare baseline characteristics of subjects with missing outcomes due to death or dropout during follow-up to detect potential violation to the missing at random assumption. Intention to treat analysis will be used in all models. Further sensitivity analyses will be performed using various methods of imputation or a full parametric likelihood approach assuming various patterns of missing data.

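### The baseline comparison of patients with missing outcomes cannot detect a violation of missing at random, and the planned sensitivity analyses are too open to fill the gap

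*Combined protocol and SAP*

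**What the plan says.** The Missing Data paragraph of Section 8 makes five statements that bear on this point.

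- Primary model: "The mixed effects model approach we propose to use is robust under the missing at random assumption", with the assumption explained as "the probability of missing is unrelated to the missing observations".
- Deaths: "We do not expect rates of death to differ among the four randomized groups".
- Withdrawals: "There may be a potential for higher rate of withdrawal in those enrolled in the intervention groups than in the control group". No rates by arm are given.
- Diagnostic: patients whose outcomes are missing through death or dropout will have their baseline characteristics compared "to detect potential violation to the missing at random assumption". The comparison group is not named, and nothing says whether it is done by arm.
- Sensitivity: "Further sensitivity analyses will be performed using various methods of imputation or a full parametric likelihood approach assuming various patterns of missing data". No method, mechanism, size of departure or arm-specific assumption follows.

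The Primary Specific Aim paragraph of the same section adjusts the mixed model for the stratification variables and for baseline covariates that prove significantly different in univariate comparisons. Under the Sample Size and Power paragraph, 30% of patients may miss some post-baseline assessments, and outcomes correlate 0.2 when 3 months apart and 0.1 when 6 months apart.

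**The concern.** By the plan's own definition, MAR fails when missingness is related to the values that were not observed. A table of baseline characteristics contains only observed values. It can show that missingness is not completely at random, which is a different matter.

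The check can therefore mislead in both directions. A baseline difference is compatible with MAR if the variable is in the model. The absence of a difference is compatible with patients leaving because of how they were doing at 3 months.

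The result also has no stated consequence. Covariates enter the model for differing between the randomized groups, not for predicting dropout, so the one sound use of the comparison is not planned.

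At stake is the training-versus-control contrast. If poor performers leave a training arm more often than the attention-control arm, the mixed model overstates the training effect, and a quiet baseline table would be read as support for MAR.

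**Working it through.** **Inputs from the documents.** 86 per group; correlation 0.2 between baseline and 3 months, 0.1 between baseline and 6 months; assumed effects 0.4 SD (single intervention) and 0.8 SD (combined); 30% missing overall.

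**Assumptions, not in the documents.** Dropout rates by arm, the strength of the link between score and dropout (logistic slope per SD), and that low scorers are the ones who leave.

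**The plan's own figures reproduce.** 60/(1 − 0.30) = 85.7, rounded up to 86; 4 × 86 = 344. A noncentral F calculation for the four-group by three-time interaction with 60 per group gives 83.3% power against the stated 83%. The sample size is not at fault.

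**What baseline RBANS can carry.** At the planned correlations it explains 0.2² = 4% of the 3-month variance and 0.1² = 1% of the 6-month variance. It can do little to reveal or correct outcome-driven dropout.

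**Size by formula.** If completers exceed dropouts by δ in both arms, given what is modelled, the bias in the arm difference is δ × (p_training − p_control). With 30% and 15%:

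- δ = 0.3 SD: 0.3 × 0.15 = 0.045 SD
- δ = 0.5 SD: 0.5 × 0.15 = 0.075 SD
- δ = 0.8 SD: 0.8 × 0.15 = 0.12 SD

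**Simulation, 15% control versus 30% training.** Two arms of 86, no true effect, slopes 0.7 to 1.5 per SD. The diagnostic is a t-test of baseline RBANS, dropouts against completers. The estimate is the completers' 3-month difference adjusted for baseline.

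| Dropout driven by | Check significant | Bias (SD) | Type I error |
|---|---|---|---|
| Baseline score only (MAR holds) | 93–100% | essentially 0 | – |
| Unseen 3-month score | 10–22% | 0.09–0.15 | 8–17% |

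A likelihood estimate that treats baseline as an outcome, closer to the planned model, gave the same 3-month bias (0.09 to 0.15 SD). Its 6-month bias was at most 0.03 SD, because dropout was tied to the 3-month score.

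**Simulation, other assumed rates (slope 1).**

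| Dropout driven by | Control/training rates | Check significant | Bias (SD) |
|---|---|---|---|
| Baseline score only | 20%/40% | about 100% | 0.00 |
| Unseen 3-month score | 20%/40% | 17% | 0.15 |
| Part of that score not explained by baseline | 20%/40% | 5.5% (chance level) | 0.15 |
| Same, training arm only | 20%/40% | 5.5% | 0.32 |
| Unseen 3-month score | 25%/35% | 16% | 0.08 |
| Unseen 3-month score | 30%/30% | 18% | 0.00 |
| Part not explained by baseline, training arm only | 30%/30% | 5.2% | 0.25 |

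The bias comes from a difference between arms in dropout rate or mechanism. Where both are equal it cancels.

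**Why a difference between arms is plausible.** From Section 5, the combined arm is asked for (2 + 3) × 45 = 225 minutes a week; the two control activities come to at most 2 × 20 + 3 × 10 = 70.

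**The case against.** **The plan has a second safeguard.** Sensitivity analyses follow in the same paragraph, and their closing words about different patterns of missing data can be read as including missing-not-at-random models. This stands: a reader might infer that the baseline comparison is all the plan relies on, and the text does not support that. What remains is that the sentence could be met entirely by MAR imputation, which does not test MAR. Nothing ties it to unequal withdrawal, and the choice of method stays open until the data are seen.

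**Higher withdrawal is not a forecast.** A reader might infer that the plan expects it. The wording only allows for the possibility.

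**The comparison has real value.** It covers baseline characteristics in general, and Section 9 lists many, such as APACHE II, Charlson, IQCODE and education. If one of these drives dropout, predicts RBANS and is outside the model, the planned analysis is biased and the check will show it. With an assumed correlation of 0.5 between such a covariate and the 3-month score, and 15% versus 30% dropout, a check on that covariate flagged about 100% of trials, with a bias of 0.05 to 0.08 SD that adjustment removed. This stands, and is the reason to give the comparison a consequence rather than drop it.

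**Low detection depends on the inputs.** With a baseline correlation of 0.6 to 0.7 (an assumption; the documents give 0.2), the check flagged 54 to 99% of the outcome-driven cases and the bias fell to 0.05 to 0.11 SD. A second baseline variable correlated 0.5 with the outcome raised detection to 40 to 85%. This stands as a limit on the detection figures. A flag still would not tell outcome-driven from baseline-driven dropout.

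**Mitigation exists.** Section 5 offers a step-down battery (also by phone), payments tied to the 3- and 6-month assessments, make-up sessions, and staff follow-up if retention drops below 80%. These may reduce missingness; they do not test the assumption about what is still missing.

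**Conclusion.** The concern holds in a limited form. The only diagnostic named for violation of MAR cannot detect it, its result leads to no stated action, and the sensitivity analyses are planned but unspecified.

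Under the assumed 15% versus 30% dropout with low scorers leaving, the bias in training versus control at 3 months is about 0.09 to 0.15 SD, roughly a quarter to a third of the assumed 0.4 SD single-intervention effect (0.09/0.4 = 0.23; 0.15/0.4 = 0.38 at the upper end). A baseline RBANS check would be significant in about 10 to 20% of such trials. Rates by arm, strength and direction are all assumptions; if high scorers left instead, the sign would reverse.

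A reader might infer that every combined-arm contrast is overstated. The documents do not support that. Their withdrawal concern sets the intervention groups against control, and combined versus a single-intervention arm shows no bias if both lose patients at the same rate by the same mechanism. Sample size and power are unaffected.

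**What to change.** 1. Delete the claim that the baseline comparison detects violation of MAR. Run it by arm, name the comparison group, and use it to identify baseline predictors of missingness that enter the mixed model or the imputation model, in addition to the present rule based on differences between groups.
2. Keep the planned sensitivity analyses and add one prespecified missing-not-at-random analysis. One suitable choice is arm-specific delta-adjusted multiple imputation (tipping point) for combined versus each other arm at 3 and 6 months. Fix the range of shifts in advance, for example 0 to −0.8 SD for training-arm dropouts, and report the shift at which the conclusion changes. A control-based pattern-mixture analysis would be a reasonable alternative.

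The cost is SAP wording and extra model runs on data already being collected.
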